Biofeedback therapy improves corticoanal function²⁶ and it alongside of medical management, is the mainstay of treatment of DD. Its main advantages are that it is noninvasive, free of morbidity and with a documented success rate of over 70%¹⁶. The short-term success rate for biofeedback therapy depends on the patient's motivation, the operator's expertise and skills, and the quality of their interaction with the patient. Successful protocols from tertiary centers have used 5-6 treatment sessions, lasting 30-60 minutes each at two weekly intervals¹⁷. While the short-term success rates support the use of biofeedback, there is a high failure rate of about 50%-70% at one year. The main drawbacks of biofeedback for ODS are the facts that it is expensive, time-consuming, and it has decreased availability and inconsistent outcomes which are very provider dependent. Because it is delivered in multiple clinic sessions, it is associated with a poorer patient compliance.

There is no current standard of care for patients with refractory defecatory disorders who fail a trial of medication and biofeedback therapy. Options are limited to sacral nerve stimulation, botulinum toxin injection or surgical interventions. Patients who fail, refuse or do not finish biofeedback therapy may be offered botulinum toxin injections into the puborectalis muscle³⁶. Sacral nerve stimulation has recently been proven to work for patients with defecatory disorders accompanied by rectal hyposensitivity, but studies are very small, uncontrolled and the response to treatment is inconsistent²⁷. Studies assessing the value of partial division of the puborectalis muscle reported mixed results and permanent complications, including incontinence for gas, mucus or feces^{29,37}. Total abdominal colectomy with ileorectal anastomosis is the surgical option reserved for patients with chronic constipation who have failed medical therapy. Preliminary studies have shown that it offers significant symptomatic improvement³⁵, however, like any major surgical procedure, there is a higher risk for complications. An end ileostomy or, if colonic transit is normal, a colostomy are the options of last resort for most patients.

b. Previous clinical studies

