Patients treated with Botox will have an improvement in the Altomare Obstructed Defecation Syndrome score (ODS-S) and Patient Assessment of Constipation- Quality of Life Score (PAC-QoL) compared to the placebo group.

III.SUBJECT SELECTION

a. Inclusion/exclusion criteria

Inclusion criteria

- Males and females older than 18 years of all races and backgrounds
- Competent to give informed consent
- Meet the Rome III diagnostic criteria for functional constipation
- Inability to relax the puborectalis muscle at electromyography
- Altomare Obstructed Defecation Syndrome score of 15 points or above
- Failure of treatment with 2 conservative measures which may be as follows:
 - 1 laxative (osmotic or stimulant) for 2 weeks
 - 1 fiber supplement for one month
 - o And/or trial of biofeedback for at least 4 sessions

Exclusion criteria

- Previous treatment with botulinum toxin (possible antibodies)
- Known hypersensitivity to any of the components of the toxin
- Presence of allergy or allergic reaction to bupivacaine
- Medication regimen includes narcotics
- Previous radiation therapy to the anal canal and rectum
- Prior proctectomy
- Presence of unhealed and symptomatic anal fissure
- Presence of anal pain
- Presence of fecal incontinence
- Presence of full thickness rectal prolapse
- Presence of internal sphincter myopathy
- Inflammatory bowel disease or proctitis
- Pregnancy or breast-feeding
- Subject is currently enrolled/ just finished participating in a clinical trial in which the intervention/ its carry-over effect may interact with the intervention in this trial

b. Source of subjects and recruitment methods

All patients seen through the Pelvic Floor Disorder Service in colorectal surgery and gastroenterology at MGH who are diagnosed with outlet obstruction will be told about the option to participate in the study by their treating physician/ nurse practitioner.

IV. SUBJECT ENROLLMENT

a. Methods of enrollment

We will enroll 23 patients into the control and 23 patients into the placebo arm of the study. All patients with ODS who are evaluated in the Pelvic Floor Disorders Service at MGH through colorectal surgery and gastroenterology will be informed of the study.

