All patients considered for the study will undergo pretreatment evaluation as per standard of care. This includes a history, clinical examination, and anorectal manometry. Once the patient is deemed eligible to participate, s/he will be offered the opportunity to participate in this trial.

If interested, s/he will meet with the Principal Investigator and/or research nurse practitioner to find out more about this trial. At this time all questions will be answered. Afterwards, s/he will be offered an informed consent form, for review at home. Patients will then be scheduled for a follow-up visit to review and sign consent with PI or study nurse practitioner.

Once all questions are answered and consent is signed, patients will be asked to fill out baseline questionnaires at the visit when consent is signed.

All questionnaires used in this study include validated scores. They will be used to assess the efficacy of the intervention in providing symptomatic improvement and improved quality of life (Altomare ODS score, generic SF-36 version 1, Patient Assessment of Constipation- Quality of Life questionnaire). We will also use 2 standard questionnaires to assess for Botox-specific adverse effects (Cleveland Clinic Fecal Incontinence Score and Fecal Incontinence Quality of Life Scale).

Patients will receive the questionnaires at baseline and then be asked to complete them at their one month follow-up visit.

At one month follow-up visit, patients will meet with their surgeon and the study nurse practitioner. They will first review any adverse reactions which they may have had. Patient will also be asked

about any adverse reactions which will be documented at that visit. They will then undergo anorectal manometry and fill out the questionnaires.

At 3, 6, and 12 months after the injection, patients will be mailed questionnaires. Those participants who do not respond within a month will be contacted by phone to increase response rate.

b. Drugs, devices and surgical procedures to be used

Patients are divided in 2 groups: Group #1: Placebo

Placebo consists of normal saline and has the same method and route of administration as the active treatment.

Group #2: Botox 100 IU

Each patient in Group #2 will receive a total of 100 units of botulinum toxin, stored in the research phramacy and dispensed to the clinic on the day of the procedure. Botox will be resuspended in 5 ml of sterile saline to a final concentration of 20 U/ml.

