For both groups, the interventions will be administered in the office under local anesthesia with 0.25% Marcaine stored in the clinic at 20° to 25°C. We plan to use a 10 mL single dose vial of Marcaine (Bupivacaine Hydrochloride Injection, USP 0.25% (2.5 mg/mL)) administered as local infiltration. More or less drug may be used depending on each individual case. The MGH **Research** Pharmacy will perform the computerized randomization and send up medication or saline in paper bag based on randomization of the subject. Both saline and Botox will be brought from research pharmacy on the day of the procedure in a brown paper bag.

The PI will use transanal ultrasound to clearly identify the puborectalis muscle. Once the muscle is identified, a 23-G needle will be used to inject the agent transanally into the puborectalis and external anal sphincter in three separate locations.

c. Data to be collected

All data are collected prospectively, at the pre-specified time points according to the protocol. All data will be collected in questionnaires attached (see above for specific description). Data from baseline manometry will be taken from patient chart and recorded into REDCap database where data will be stored. Anorectal manometry from 1-month follow-up will also be stored in REDCap database.

VI. BIOSTATISTICAL ANALYSIS

a. Specific data variables being collected for the study

Data collection sheets are attached to this submission. They include the MRN to facilitate data extraction, demographic information (age, sex, race), diagnostic tests at baseline and the study endpoints collected at pre-specified times.

b. Study Endpoints

a) Primary endpoint:

Baseline to 1 month after treatment changes in the sum of Altomare ODS score (ODS-S) and Patient Assessment of Constipation- Quality of Life score (PAC-QoL)

b) Secondary endpoints:

- Baseline to 1, 3, 6 and 12 months after treatment changes in Altomare ODS score (ODS-S) and Patient Assessment of Constipation- Quality of Life score (PAC-QoL)
- Changes in the generic SF-36 version 1, Cleveland Clinic Fecal Incontinence Score (CCFI) and Fecal Incontinence Quality of Life Scale (FIQoL) at 1, 3, 6 and 12 months from baseline
- Relaxation of puborectalis with push measured by EMG at 1 month
- Balloon expulsion test at 1 month
- Manometric changes at 1 month- changes in anal sphincter function (resting sphincter pressure, maximal resting anal pressure, maximum squeeze pressure).

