- Change in defecation index [Time Frame: Baseline, 1 month follow-up visit]. The defecation index=maximum rectal pressure during attempted defecation/minimum anal residual pressure during attempted defecation. This is calculated based on measurements obtained from anorectal manometry and is a measure of treatment efficacy.

c. Statistical methods

All analysis will be based on intention-to-treat population in that all randomized subjects will be included in the analysis.

Data will be expressed as mean+/- standard deviation (SD) for all continuous outcomes, and as counts and proportions for all categorical outcomes. The primary analysis (i.e., the comparison of 1-month change in mean ODS-S and PAC-QoL between the 2 treatment arms) will be made by independent samples t-test. Comparison of treatment effect over time (i.e., 1- and 3-, 6- and 12 months) on all scale scores will be performed by using longitudinal linear mixed effects model, which allows to specify the subject specific baseline levels and the time dependent response trajectories (i.e., slopes) random (SAS proc mixed). All p-values are two-tailed and considered significant if p<0.05.

d. Power analysis

The proposed sample size is 46 (i.e., 23 in each treatment arm). With an assumption of an attrition rate of up to 15%, we anticipate to attain 40 study completers. The study is designed to detect at

least 25% decrease in mean ODS-S and PAC-QoL at 1 month after treatment with Botox with 80% power at a 5% significance level. This effect size of \geq 25% is equivalent to a decrease in mean ODS-S decrease from 15 points at baseline to \leq 11.4 points at 1 month³⁷⁻³⁸. **VII. RISKS AND DISCOMFORTS**

a. Complications of surgical and non-surgical procedures

We do not expect any unusual safety concerns in this study. The small foreseeable discomforts and complications will be treated as per standard of care.

b. Drug side effects and toxicities

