Botulinum toxin (Botox) has been shown to be very safe and well-tolerated in prior studies, however variable doses of Botox were previously shown to have efficacy. Concerns may arise for potential issues with incontinence for gas, liquid or solid stool if higher doses of Botox are studied. The reported incidence of incontinence has been low in previous studies and it was mostly mild (gas>soling>solid stool). If incontinence occurs, it may cause significant discomfort to patients who work in a public place and could account for a low recruitment rate and unblinding of patients who experience these adverse effects. Both the active treatment and placebo groups receive transanal injections into three sites. This can cause local discomfort/pain so we will co-administer a long-acting local anesthetic. Patients will also be given instructions to take ibuprofen or acetaminophen as needed for pain relief after procedure. There is the additional risk of infection at the site of injection. The risk of this is low, but all patients will be instructed to call with any symptoms of infection, and will be seen by PI or research nurse practitioner and treated as necessary.

c. Device complications/malfunctions

Not applicable

d. Psychosocial (non-medical) risks

Psychosocial risks may include loss of productivity from appointments. We tried to limit this by administering our surveys via mail and phone and by asking the patients to come in only for the consent, intervention and one visit at 1 month afterwards.

Patients who are in the control group may experience frustration with lack of improvement of their symptoms and frustration from the need to undergo further treatments and investigations at the end of the study. We tried to address this issue by encouraging all patients to receive the standard of care (biofeedback) prior to treatment. Also, at the end of the study, if the medication demonstrates efficacy for ODS, patients in the control group will be offered the option to receive Botox. These patients will be monitored per described plan for this study, but the subjects and investigator will no longer be blinded.

It has been reported that patients enrolled in clinical trials are often frustrated by not knowing the results of their tests and the outcome of the study. To address this, patients will receive a written report of their objective measures (EMG, anorectal manometry, balloon expulsion test) at the one

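### Manometric and defecation-index endpoints are raw changes from an undated chart baseline; comparing 1-month values adjusted for that baseline would be more precise at almost no cost

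*Combined protocol and SAP*

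**What the plan says.** **Source of the baseline.** Section V.c: "Data from baseline manometry will be taken from patient chart and recorded into REDCap database where data will be stored". The test belongs to routine work-up. Section V.a states "All patients considered for the study will undergo pretreatment evaluation as per standard of care" and adds "This includes a history, clinical examination, and anorectal manometry". This comes before eligibility is settled and before consent. Neither section gives a maximum age for the test, a repeat test, or an order relative to biofeedback. The questionnaires are treated differently, because section V.a says "patients will be asked to fill out baseline questionnaires at the visit when consent is signed". The only manometry placed at a study visit is the one at 1 month.

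**Biofeedback before injection.** It is one optional route to eligibility (section III.a: "And/or trial of biofeedback for at least 4 sessions"). Section VII.d describes "encouraging all patients to receive the standard of care (biofeedback) prior to treatment". Section I.a states "Biofeedback therapy improves corticoanal function".

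**Endpoints.** Section VI.b lists 1-month changes in resting and squeeze pressures as secondary, together with "Change in defecation index [Time Frame: Baseline, 1 month follow-up visit".

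**Analysis.** Section VI.c gives a t-test for the primary endpoint and a mixed model for scale scores over time. It names no method for the manometric endpoints and mentions no baseline adjustment for any endpoint.

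**The concern.** A change score takes the chart value at full weight, which works well only when that value tracks the 1-month value closely. Here the interval between the two tests is not controlled, and for some patients it may contain a course of biofeedback. Either feature can lower the correlation between the two measurements, and subtraction then adds variance instead of removing it.

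Section VI.d expects 40 completers, about 20 per arm, so precision is scarce. The manometric endpoints are the plan's objective evidence of what the injection does, and section VI.b presents the defecation index as an efficacy measure. A noisy analysis could leave these endpoints uninformative when the same data, analysed differently, would say more.

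**Working it through.** **Inputs from the documents.** 46 randomised 1:1, attrition up to 15%, 40 completers, two-sided 5% level (sections IV.c, VI.c, VI.d). Check of the plan's figure: 46 × 0.85 = 39.1, against 40 stated, which is close enough. I use 20 per arm. The stated 80% power concerns ODS-S and PAC-QoL only. It cannot be reproduced because no SD is given, and nothing below depends on it.

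**Assumptions.** The documents give no SD or correlation for any manometric measure. I take equal variance (set to 1) at both times and let the baseline/1-month correlation r range from 0.3 to 0.7.

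**Variance per patient of the three possible analyses**

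- Change score: 2(1 − r)
- 1-month value, unadjusted: 1
- ANCOVA on baseline: 1 − r²
- ANCOVA relative to change: (1 − r)(1 + r) / [2(1 − r)] = (1 + r)/2

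| r | Change | 1-month only | ANCOVA | ANCOVA / change | Patients under ANCOVA matching 40 under change |
|---|---|---|---|---|---|
| 0.3 | 1.40 | 1 | 0.91 | 0.65 | 26 |
| 0.5 | 1.00 | 1 | 0.75 | 0.75 | 30 |
| 0.7 | 0.60 | 1 | 0.51 | 0.85 | 34 |

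The change score is worse than ignoring the baseline when 2(1 − r) > 1, that is, when r < 0.5.

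**Detectable difference.** With 20 per arm, 80% power and a two-sided 5% t-test, the detectable standardised difference is 0.909. Multiplying by the square root of each variance gives, in SD units and ignoring the degree of freedom spent on the covariate:

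- r = 0.3: 1.08 (change), 0.91 (1-month only), 0.87 (ANCOVA)
- r = 0.5: 0.91, 0.91, 0.79
- r = 0.7: 0.70, 0.91, 0.65

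**Does biofeedback after the chart test bias the comparison?** A simulation of 40,000 trials took 20 per arm, r = 0.7, a true injection effect of 0.5 SD, and biofeedback after the chart test in half of each arm, with a variable response (SD 0.5). All of these values are assumed.

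| Mean shift from biofeedback | Between-arm estimate | SE | Mean change, Botox | Mean change, placebo |
|---|---|---|---|---|
| None | 0.50 | 0.246 | 0.50 | 0.00 |
| 0.5 SD | 0.50 | 0.280 | 0.75 | 0.25 |
| 1.0 SD | 0.50 | 0.312 | 1.00 | 0.50 |

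The SEs agree with direct calculation. The variance of a change is 0.6 plus the variance added by the shift, and the SE is the square root of 2 × variance / 20.

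- 0.5 SD shift: added variance 0.5 × (0.25 + 0.25) − 0.25² = 0.1875, so SE = √(2 × 0.7875/20) = 0.281.
- 1.0 SD shift: added variance 0.5 × (0.25 + 1) − 0.5² = 0.375, so SE = √(2 × 0.975/20) = 0.312.

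The between-arm estimate does not move. The SE rises by 14% (0.280/0.246) to 27% (0.312/0.246), and each arm's own mean change takes in the biofeedback shift.

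**The case against.** The case on the other side is substantial.

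- **The comparison is randomised.** The aim and hypothesis are between-arm, so an old baseline does not bias them. This stands. Chance imbalance in biofeedback exposure is ordinary sampling error already inside the SE, not a further harm.
- **The timeline is not documented.** A reader might infer that the usual patient has manometry at diagnosis and biofeedback afterwards. No section says so. Section IV.b has patients fail medical therapy before they are screened, and section V.a ties the work-up to being considered for the study. Read together, these could place the test after conservative treatment has failed. This stands. The text leaves the order open and does not establish a stale baseline.
- **The mechanism is thin.** Section I.a refers to corticoanal function and does not mention sphincter pressures or the defecation index. Patients who qualify through biofeedback are those in whom it failed. This stands, so the size of any shift is unknown.
- **The arithmetic is generic.** The ratio (1+r)/2 applies to any change endpoint, however fresh the baseline, and nothing in the documents links chart age to r. This also stands: the ratio measures the gain from ANCOVA, not the cost of using chart data.
- **The plan does not prescribe a test of raw changes.** It names no method for manometry, and an endpoint called a change can still be analysed by ANCOVA. That is correct, but the endpoint is defined as a change and no adjustment appears anywhere, so raw change is the natural default unless the text says otherwise.
- **Dates may already be captured.** Section VI.a refers to attached data collection sheets that cover baseline diagnostic tests. They are not available here, so this cannot be settled.

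What survives is narrower and firmer: for these endpoints, adjusting for the baseline already collected is more precise than subtracting it, and the more so the weaker the correlation.

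**Conclusion.** The point holds as a matter of precision on secondary endpoints. The documents set no date window and no order relative to biofeedback for the chart manometry. They define the sphincter-pressure and defecation-index endpoints as changes from it, with no adjustment. Under equal variances and an assumed r of 0.3 to 0.7, ANCOVA cuts the variance of the arm comparison to between 0.65 and 0.85 of the change-score variance. If r is below 0.5, raw change is worse than not using the baseline. The true r is unknown. A low value is possible if some chart tests are old or precede biofeedback, but the documents do not show that they do.

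Two stronger readings are not supported. The first is that the Botox-placebo difference is confounded by earlier treatment; randomisation prevents that in expectation, and the simulated estimate stayed at 0.50. The second is that the plan will report within-arm changes as effects of the injection; no section says so, although none excludes it. The primary endpoint, its consent-visit baseline and the sample size of 46 do not depend on manometry.

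**What to change.** 1. **Sections VI.b and VI.c:** state that arms will be compared on the 1-month sphincter pressures and defecation index by ANCOVA, with the chart baseline as covariate. Where the chart holds several tests, use the last one before injection. Fix this wording before the statistician is unblinded at database lock.
2. **Section V.c, as support:** record the date of the chart manometry and whether any biofeedback took place between that test and the injection, if the existing collection sheets do not already do so. The biofeedback indicator may be added as a second covariate. It should stop at the injection, because biofeedback after that point could itself be affected by treatment.
3. **Interpretation:** state that only the between-arm contrast will be read as the effect of the injection. Within-arm changes are descriptive.

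The cost is one or two model degrees of freedom, up to two data fields and a few lines of text. No additional test, visit or patient is needed. The gain does not depend on any baseline being stale: at r = 0.7 the ANCOVA variance is still 0.85 of the change-score variance.

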Hompes et al. ³⁶ reported an excellent response of patients with anismus to 100 IU of Botox. Twenty-two (39%) of 56 patients responded initially and 21/22 (95%) underwent repeat injection. At a median follow-up of 19.2 (range, 7.0–30.4) months, 20/21 (95%) had a sustained response and required no further treatment. In 33 (97%) of 34 nonresponders, significant abnormalities were demonstrated at EUA: 31 (94%) had a grade 3–5 rectal prolapse, one had internal anal sphincter myopathy and one had a fissure. Exclusion of these alternative diagnoses revised the initial response rate to 96%. Of 56 patients who received the injection, 4 (7.1%) developed transient minor fecal incontinence (for gas rather than minor soiling). These adverse effects occurred in 4/16 patients who ultimately proved to have rectal prolapse. No Patient with ODS alone had any continence disturbance.

In summary, doses between 50-100 IU of Botox are safe, well tolerated and have been shown in small studies without blinding to provide immediate symptomatic relief in the majority of patients with ODS constipation. For those who did not respond to low doses, higher doses of 100 IU have been used successfully, with improvement in 90-100% of the cases. Based on the available evidence, Botox is a reasonable therapeutic option after failure of conservative management and before more invasive surgery is attempted ³⁴.

c. Rationale behind the proposed research and potential benefits to patients and society

ODS is an undertreated condition, whose prevalence increases with age and is predicted to increase dramatically with the aging population. Botox has been proposed as an effective treatment and it has long been used off-label in ODS patients who refused or failed medical management and biofeedback therapy. However, to this day, no randomized controlled trial has confirmed that Botox is superior to placebo for the treatment of ODS.

We will use 100 IU of Botox, a dose with a good safety profile that has been proven to work in previous studies. We want to evaluate the efficacy of Botox 100 IU compared to placebo in addition to the standard of care (biofeedback therapy) in the treatment of patients diagnosed with ODS. We also plan to document patient compliance with biofeedback therapy.

II. SPECIFIC AIMS

Objective:

To evaluate the efficacy and safety of Botox for the treatment of ODS.

Hypotheses:

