On the day of the procedure, the research nurse will obtain the saline or Botox from the research pharmacy in a brown paper bag. She will then prepare the Botox or draw the normal saline and give it to the investigator for administration. In order to protect blinding, placebo and Botox will have the same characteristics, except for the active drug. The nurse who prepares the drug will also record the study arm in a file kept separate from patient information. Once this is recorded, information will be resealed and kept with patient information until the completion of the study. The nurse who prepared the composition will be the only unblinded member of the healthcare team and will not assist in the procedure.

The adverse effects will be assessed by one standard questionnaire, which allows the description of idiosyncratic reactions and 2 validated questionnaires, which assess the Botox specific adverse effects of fecal incontinence. Outcome measurements and assessment of adverse effects in the office will be made by a research nurse blinded to treatment group allocation.

The PI who delivers the intervention will not take outcome measurements and will have no interaction with the data collectors. The data collectors will be blinded throughout the data entry and data cleaning processes. The statistical analysis will be made after the end of the data collection period. The statistician will only be unblinded once the database is locked. At the end of the study, blinding integrity will be evaluated in a sample of participants and data collectors.

In case of medical emergency, if a study participant has encountered an urgent medical problem and the clinician needs to know his/her intervention group, the allocation code can be broken. Unblinding envelopes (labeled with the randomization number that contains allocation) are sealed by the study center and are only opened if emergency unblinding is necessary.

V. STUDY PROCEDURES

a. Study visits and parameters to be measured

As part of this research study, patients will be asked to come for three visits (Visit 1= return of informed consent and schedule of intervention; Visit 2= intervention; Visit 3=one month after the intervention). They will afterwards be contacted by mail with questionnaires and then with follow-up phone calls (for those who did not return questionnaires) to increase response rate at 3, 6 and 12 months after the intervention.

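### New fecal incontinence, the named Botox-specific harm, has no planned per-arm case count; its only stated analysis is change in scale scores, where a few cases hardly show

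*Combined protocol and SAP*

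**What the plan says.** - Section II states one objective: "To evaluate the efficacy and safety of Botox for the treatment of ODS".
- Section III.a lists "Presence of fecal incontinence" among the exclusions. It gives no score cut-off and does not say whether leakage of gas counts.
- Section IV.c describes how harms are captured: "The adverse effects will be assessed by one standard questionnaire, which allows the description of idiosyncratic reactions and 2 validated questionnaires". The two validated instruments are for incontinence. Section V.a gives them the same role: "We will also use 2 standard questionnaires to assess for Botox-specific adverse effects".
- Section V.a also has patients asked, at the 1-month visit, "about any adverse reactions which will be documented at that visit". After that visit it describes only mailed questionnaires, with telephone follow-up of non-responders.
- Section VI.b lists, as secondary endpoints, changes in SF-36 and in "Cleveland Clinic Fecal Incontinence Score (CCFI) and Fecal Incontinence Quality of Life Scale (FIQoL) at 1, 3, 6 and 12 months from baseline".
- Section VI.c says: "Data will be expressed as mean+/- standard deviation (SD) for all continuous outcomes". Categorical outcomes are to be given as counts and proportions, but adverse events are not named among them. All scale scores go into a linear mixed model over 1, 3, 6 and 12 months.

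Neither VI.b nor VI.c defines a case of new incontinence, counts such cases by arm, or states an analysis of the adverse-effect questionnaire.

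**The concern.** Change in mean score suits the efficacy scales, where every patient enters with symptoms and most can move. Incontinence differs. If patients enter largely continent, they can only stay as they are or worsen, and the harm would appear as a few patients with a rise among many with none. A mean and SD describe such data poorly, and a test on the mean is insensitive to them.

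Section I.b describes the earlier cases as transient or mild, with muscle recovery over 2 to 4 months, so few patients may be affected at any one visit. The risk lies in the reporting: a non-significant change in CCFI or FIQoL could be read as reassurance on the one harm for which the protocol provides dedicated instruments, while the number of patients affected is never set out.

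**Working it through.** The plan gives no sample-size or precision figure for safety, so there is none to reproduce. Section VI.d sizes the trial (23 per arm, about 40 completers in total) for ODS-S and PAC-QoL only.

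**1. What a few cases do to a mean.** Assume that k of n = 23 Botox patients rise by the same d points and that all other patients in both arms stay at 0.

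- Mean change = kd/n; SD = d × √[k(n−k)/(n(n−1))].
- Two-sample t against an arm of zeros = √[k(n−1)/(n−k)], with 44 degrees of freedom. The rise d cancels.

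| Cases (of 23 vs 0 of 23) | Mean (SD) if d = 4 | t | t-test p | Fisher p | Exact 95% CI, Botox arm |
|---|---|---|---|---|---|
| 0 | 0 | – | – | 1.00 | 0 to 14.8% |
| 2 | 0.35 (1.15) | √(44/21) = 1.45 | 0.155 | 0.49 | 1.1 to 28.0% |
| 3 | 0.52 (1.38) | √(66/20) = 1.82 | 0.076 | 0.23 | 2.8 to 33.6% |
| 4 | 0.70 (1.55) | √(88/19) = 2.15 | 0.037 | 0.11 | 5.0 to 38.8% |
| 5 | 0.87 (1.69) | √(110/18) = 2.47 | 0.017 | 0.049 | 7.5 to 43.7% |

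The 4-point rise is an assumption that affects only the mean and SD. Two patients with a severe rise and two with a slight one give the same p-value. The upper limit for 0/23 is 1 − 0.025^(1/23) = 14.8%; with 20 completers in the arm, 0/20 gives 16.8%.

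The t-test is a stand-in for a comparison of means at 1 month. The plan assigns it only to the primary analysis, and the planned mixed model was not simulated.

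**2. Which rates the documents support (section I.b).**

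- No incontinence: the 100 IU arm of the three-arm randomised comparison, the 20 IU randomised study, and the 25 IU series (no adverse effects at all).
- 4/56 = 7.1%: the 100 IU series. All four cases proved to have rectal prolapse, and none occurred with ODS alone.
- 2/24 = 8.3%: the 60 IU series, mild and flatus only.
- 2/7 = 28.6%: the 1988 pilot, which used several doses.

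Applied to 23 patients, these span 0 to 23 × 2/7 = 6.6 cases. No single expected count follows. At 7.1% to 8.3% the expectation is 1.6 to 1.9 cases, with an 82% to 86% chance of at least one and 49% to 58% of at least two.

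**3. Power of either approach.** This was simulated with 23 per arm, no events on placebo, assumed rises of 2 to 12 points, and noise SD of 0 or 1.

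- At 7.1% to 8.3%: t-test on mean change about 7% to 14%; Fisher test on counts 2% to 4%.
- At an assumed 25%: t-test 29% to 87%; Fisher 72%.

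At low rates neither approach detects a difference. At high rates the mean-based analysis is not blind.

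**The case against.** The strongest reply is that a reader might infer that safety is judged only on mean change, and no section says so. The open adverse-effect questionnaire and the documented 1-month review would record new cases patient by patient, close to the time when section I.b expects weakness to develop (2 to 20 days). A yes/no event would also fit the rule that categorical outcomes are given as counts and proportions. This stands: cases need not be lost. But these data have no stated endpoint, case definition or analysis, and VI.c does not name them.

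Four further objections also stand in whole or part:

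- The near-continent baseline is inferred. No cut-off, baseline value or rule on gas is given.
- It is tempting to expect about two cases from the 7% to 8% rates. Those are two of several figures. The four cases in the 56-patient series all had prolapse, and full-thickness prolapse is excluded here.
- It is also tempting to say that the analysis averages a transient effect away over 12 months. VI.b lists change at each visit, and VI.c models the effect over time with subject-specific slopes; averaging over visits is not stated.
- Counting cases is no more powerful: 2/23 against 0/23 gives Fisher p = 0.49, and five cases against none are needed for p < 0.05. The limit is the sample size, which was not chosen to detect incontinence.

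**Conclusion.** The point holds as a gap in the planned safety summary. Safety is in the objective and incontinence is the named harm, yet its only pre-specified analysis is change in two scale scores. Two or three new cases in 23 would leave a mean change of about half a point or less (for an assumed 4-point rise) and a t-test p of 0.155 or 0.076, while the corresponding proportions have upper limits of 28.0% and 33.6%. The p-values rest on near-zero baselines, equal rises and no change in other patients; the exact intervals do not.

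The documents do not support the stronger conclusion that the trial cannot answer its safety objective or that cases would go unrecorded. Nor do they support any particular expected number of cases. What is missing is a defined, per-arm count with its uncertainty, so that a null result on the mean is not taken as evidence of safety.

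**What to change.** In VI.b, add as the main incontinence safety summary the number and proportion of patients per arm with new or worsened incontinence relative to baseline. Define a case before any unblinding, including any unblinding for the half-recruitment review in IX.a, from a stated rise in CCFI or from incontinence reported as an adverse effect at 1 month. Say whether gas alone counts, and choose the rise so that trivial fluctuation in either arm is not a case.

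In VI.c, report the count at 1 month and cumulatively to 3 months, with the number of patients assessed and exact 95% confidence intervals for each arm and for the difference. The 3-month part would come from the mailed CCFI, because adverse-reaction review is described only at 1 month. Keep mean CCFI and FIQoL change as descriptive, and base the safety wording on the upper confidence limit.

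The cost is a few lines of text. The data are already to be collected, and the sample size and primary analysis do not change. The downside is a wide interval and a less favourable-looking safety statement. A case that begins and resolves between the 1- and 3-month assessments could still be missed.
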